5.5.2.1 Frequency and prevalence of adverse events

AEs are summarized according to both frequency and prevalence and based on various grouping terms (for example MedDRA preferred term, or MedDRA primary system organ class).

For frequency of subjects experiencing an AE, AEs reported more than once for a subject (based on grouping term) are counted only once per subject.

For total cumulative number of events, multiple records of the same MedDRA preferred term in the AE dataset for the same subject count as individual events (episodes of the same type of event) unless they have the same start date and – if available – time.

The observation time (in days) per subject for summaries of treatment-emergent AEs is calculated as: minimum (EOT + 15, EOS) – study treatment start date + 1.

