5.5.9.2 Major adverse cardiovascular events (MACE)

Based on a pre-defined list of preferred terms belonging to relevant Standardized Medical Dictionary for Regulatory Activities Queries (SMQs), AEs are selected for the MACE adjudication board evaluation. For each case sent for MACE adjudication, the board members individually assess whether the case is a myocardial infarction, a stroke, or another adverse event. For fatal cases, each member determines whether the death is considered of cardiovascular, non-cardiovascular, or undetermined cause. If not all individual assessments concur, the case is classified into the above listed categories based on a consensus meeting. For data analysis, each case is assigned to one of the following categories:

- cardiovascular death (if a death case is classified as cardiovascular)
- non-fatal myocardial infarction (if the case is classified as myocardial infarction but not as cardiovascular death)
- non-fatal stroke (if the case is classified as stroke but not as cardiovascular death)
- no MACE (if the case is classified as other adverse event, but not as cardiovascular death)

The onset date and treatment-emergent status of a MACE is determined by the onset date and treatment-emergent status of the corresponding AE. In case more than one AE is linked to the same MACE case, the earliest treatment-emergent AE onset date determines the MACE onset date; if none of the linked AE is considered treatment-emergent, the earliest AE onset date determines the MACE onset date. This may lead to cardiovascular death MACE with an onset date prior to the date of death.

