9.10.2.4 Other significant adverse events

9.10.2.4.1 Adverse events of special interest (AESIs)

For each of the AESI categories described in Section 5.5.9.1, the following information is presented: The number and percent of subjects with AESI is summarized by preferred term per treatment arm. In addition, the number and percentage of subjects having any event of that category, having any serious event, any fatal event or any event leading to premature discontinuation of study drug, the relative risk relative to teriflunomide (incl. 95% CI). The table will also include key estimates from a time to first event analysis (Kaplan-Meier estimates and hazard ratio along with 95% CI), the number of occasions (i.e., recurrent events) and corresponding cumulative subject-years of observation, and based on Poisson regression, the average annualized event rate and rate ratio with corresponding rate ratio incl. 95% CI. Corresponding time to first event (Kaplan-Meier) curves (going upwards) are graphically displayed as described in Section 10.4. Separate listings are prepared on the FAS.

These tables and graph are presented for the following subcategories:

- Treatment-emergent AESIs, based on the SAF for each AESI category separately;
- Hepatobiliary disorders / Liver enzyme abnormality AESI that occurred after start of study drug and up to and including EOT + 1 day

In addition, treatment-emergent AESI Effect on heart rate and rhythm related AEs are summarized by time of onset by presenting, per treatment group, the number and percentage of subjects having any AE, and having each individual AE (preferred term). Preferred terms are sorted by descending order of frequency in the ponesimod arm. This analysis is done

- By day of onset after study start, by groups: Day 1, Day 2, Day 3, Day 4, Day 5, Day 6, Day 7, Day 8, Day 9, Day 10, Day 11, Day 12, Day 13, Day 14, Day 15, Day 16, > Day 16

- By day of onset after any re-initiation of up-titration, for the following (daily) by groups: Day 1 of any re-initiation, Day 2 of any re-initiation... , Day 16 of any re-initiation

9.10.2.4.2 *Major adverse cardiovascular events (MACE)*

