Based on the SAF, treatment emergent MACEs are summarized by presenting, per treatment group, the number and percentage of subjects having any MACE, and having an event of the MACE subcategories (cardiovascular death, non-fatal myocardial infarction, non-fatal stroke), and the relative risk relative to teriflunomide (including 95% CI). The table will also include key estimates from a time to first event analysis (Kaplan-Meier estimates and hazard ratio along with 95% CI), the number of occasions (i.e., recurrent events) and corresponding cumulative subject-years of observation, the average annualized event rate and corresponding Poisson rate ratio including 95% CI. Corresponding time to first event (Kaplan-Meier) curves are graphically displayed as described in Section 10.4. A listing is prepared.

9.10.3 **Electrocardiography (ECG)**

The following summary displays are provided by treatment group, all based on the SAF:

- Quantitative ECG results and absolute change from baseline, as described in Section 5.5.11.1, are summarized, by parameter and visit. Except for data summarized under ‘Baseline’, ‘Day-15 follow-up’ and ‘Day-30 follow-up’, only treatment-emergent results from nominal scheduled visits are included, premature EOT visit is mapped to a scheduled visit [see Section 11.3]. These are summarized descriptively and mean changes (with standard error) from baseline in heart rate are also presented graphically over time (plots starting with zero change at baseline);
- Quantitative ECG results and absolute change from pre-dose on Day 1, by time point (pre-dose, 1–12 hours post dose), are summarized descriptively and mean changes (with standard error) from pre-dose in heart rate are also presented graphically over time (plots starting with zero change at pre-dose), plots are only to include Hours 1–4;
- Descriptive summary statistics of quantitative ECG result and absolute change from pre-dose on Day 1 of first Re-initiation, by time point (pre-dose, 1– 12 hours post dose); Note: Data from re-initiations beyond the first are listed only;

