10.1 Statistical methodology for count data

Count data will be analyzed assuming data is negative binomially (NB) distributed.

A generalized linear model with NB distribution will be assumed.

t_j denotes the length of observation for subject j .
 Y_j denotes the counts of interest for subject j during t_j .
 μ_j denotes the mean of the NB distribution of Y_j .

The mean for the distribution of the ARR for subject j , denoted by μ_j/t_j , will be modeled by the following equation:

$$\log(\mu_j/t_j) = \mathbf{x}'_j \boldsymbol{\theta}, \text{ i.e., } \log(\mu_j) = \mathbf{x}'_j \boldsymbol{\theta} + \log(t_j), \text{ where}$$

\mathbf{x}_j is the vector denoting study treatments and covariates for subject j
 $\boldsymbol{\theta}$ is the vector of unknown fixed-model parameters.

The SAS code for the NB model with 99% CI is as follows (considered “draft” until fully validated at analysis stage):

```
proc genmod data=ADREL;
  class Treat Strat Covar;
  model COUNTS = Treat Strat Covar / dist=negbin link=log
  offset = offset;
  lsmeans Treat / cl exp alpha = 0.01 OM;
  estimate 'Ponesimod - Teriflunomide' || Treat 1 -1 / exp alpha = 0.01;
run;
```

The offset variable used will be specified per analysis (e.g. for ARR it is the log-transformed observation time, for total T1 lesions it is the log-transformed number of available MRI scans, ...).

The 'LSMEANS' statement will output the mean estimates for each of the treatment arms with 99% Wald CIs; the option OM ensures that the mean is derived for categorical covariates with weights as per observed marginal proportions.

The 'ESTIMATE' statement will output the rate ratio of the treatment effect with 99% Wald CIs. The direction of the estimate statement (governed by '1 - 1' or '-1 1') is chosen such that the rate ratio relative to teriflunomide is provided (with rate ratio < 1 indicating ponesimod is better).

To obtain 95% CIs the option alpha = 0.05 is used in the LSMEANS and ESTIMATE statements.

The number of covariates / stratification variables included in the model is different from analysis to analysis, and these are described in the respective analysis sections [see Section 9]. Interaction terms might be included in the model, depending on the analysis.

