If the NB distribution is not considered to be appropriate (e.g. due to non-convergence), other distributions such as the Poisson and zero-inflated Poisson will be explored. For the Poisson distribution, a Poisson regression is conducted with model equation identical to the one for the negative binomial regression. The SAS code is as follows (considered "draft" until fully validated at analysis stage):

```
proc genmod data=ADREL;
  class Treat Strat Covar;
  model COUNTS = Treat Strat Covar / dist=poisson link=log
  offset = offset;
  lsmeans Treat / cl exp alpha = 0.01;
  estimate 'Ponesimod - Teriflunomide' || Treat 1 -1 / exp alpha = 0.01;
run;
```

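### The AESI rate-ratio intervals come from Poisson regression on recurrent events with no stated allowance for within-subject clustering, so they will be too narrow where events cluster

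*SAP*

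**What the plan says.** SAP 9.10.2.4.1 asks, for each AESI category, for "the number of occasions (i.e., recurrent events) and corresponding cumulative subject-years of observation", followed by a rate analysis "based on Poisson regression, the average annualized event rate and rate ratio with corresponding rate ratio incl. 95% CI". The unit is therefore the event, and one subject can contribute several. The same table also carries a subject-level relative risk and a time-to-first-event hazard ratio, each with a 95% CI.

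The counting rule is in 5.5.2.1: "multiple records of the same MedDRA preferred term in the AE dataset for the same subject count as individual events". The only exception is for records of that term sharing a start date and, where available, a start time. The rule does not address different preferred terms recorded for one clinical episode.

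Section 10.1 opens with a general rule, "Count data will be analyzed assuming data is negative binomially (NB) distributed", and brings in Poisson where the negative binomial (NB) is not considered appropriate: "For the Poisson distribution, a Poisson regression is conducted with model equation identical to the one for the negative binomial regression". The accompanying code, labelled draft, contains "model COUNTS = Treat Strat Covar / dist=poisson link=log" and an offset. It has no SCALE= option, no REPEATED statement and no robust variance.

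**The concern.** An ordinary Poisson interval assumes that the variance of a subject's count equals its mean. Recurrent safety events often break this, because some subjects are prone to repeats and because one episode can generate several records.

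The AESI definitions make the second route plausible. Appendix A pools overlapping terms: several dyspnoea terms alongside lung-function terms in the pulmonary category, a broad-scope comprehensive query for hepatobiliary events, and bradyarrhythmia, syncope and hypotension terms together. Under 11.4, liver tests are repeated at up to eight between-visit time points by Week 22, so one liver episode has several chances to be recorded.

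Model fit is to be assessed for the relapse rate (9.6.3) and for the MRI lesion count (9.7.2.2). No such check is planned for the safety counts, and no reason is given for going straight to Poisson there. At stake is how the sponsor's pre-defined risks are read: an interval that is too short excludes 1 too often, in either direction.

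**Working it through.** The SAP states no AESI rate, dispersion or number of records per episode, so there is no plan figure to reproduce. Everything below that concerns these quantities is an assumption.

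**Inputs from the SAP.** 1133 subjects randomised 1:1 (section 2), taken as 566 and 567. Observation for treatment-emergent events ends at the earlier of EOT + 15 days and EOS (5.5.2.1). For a completer of 108 weeks that is (756 + 15)/365.25 = 2.11 years.

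**Interval and coverage.** With equal follow-up and treatment as the only term, the Poisson standard error of the log rate ratio is sqrt(1/E1 + 1/E2), where E1 and E2 are the event totals per arm. If the true variance is larger by a factor V, then

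coverage = 2Φ(1.96/√V) − 1.

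**Route 1: several records per episode.** If an episode yields m records, V = E[m²]/E[m].
- Assumed probabilities 0.7/0.2/0.1 for 1/2/3 records: E[m] = 0.7 + 0.4 + 0.3 = 1.4; E[m²] = 0.7 + 0.8 + 0.9 = 2.4; V = 1.71; coverage about 87%.
- Assumed 0.4/0.35/0.25: E[m] = 0.4 + 0.7 + 0.75 = 1.85; E[m²] = 0.4 + 1.4 + 2.25 = 4.05; V = 2.19; coverage about 81%.
- If a fraction q of episodes gets exactly one second term, V = (1 + 3q)/(1 + q). For q = 0.25, 0.5 and 1, V = 1.40, 1.67 and 2.00; coverage 90.2%, 87.1% and 83.4%.

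**Route 2: true recurrence.** Under a negative binomial with dispersion k and mean μ = rate × 2.11, V = 1 + kμ.

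| Assumed rate per year | k = 1 | k = 3 | k = 6 |
|---|---|---|---|
| 0.02 | V 1.04, 94.5% | V 1.13, 93.5% | V 1.25, 92.0% |
| 0.05 | V 1.11, 93.8% | V 1.32, 91.2% | V 1.63, 87.5% |
| 0.10 | V 1.21, 92.5% | V 1.63, 87.5% | V 2.27, 80.7% |

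Simulation (6,000 runs per setting) agrees with these coverages to within about one percentage point. With no clustering, simulated coverage is 94.6% to 95.4% for rates of 0.02 per year or more, so the method itself is sound when its assumption holds.

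**Rare events.** At an assumed 0.003 per year, recurrence gives V of 1.01 to 1.04 and simulated coverage of about 99%, conditional on at least one event in each arm. The ordinary interval is then not too narrow.

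**Size of the correction.** A correct interval is wider on the log scale by √V: at 0.10 per year by a factor of 1.10, 1.28 and 1.50 for k = 1, 3 and 6.

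**The case against.** Several stronger readings are tempting, and the SAP does not support them.

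- **That the MACE interval is also too narrow.** Section 9.10.2.4.2 does plan "the average annualized event rate and corresponding Poisson rate ratio including 95% CI". But MACE cases are adjudicated, and 5.5.9.2 merges linked records: "In case more than one AE is linked to the same MACE case, the earliest treatment-emergent AE onset date determines the MACE onset date". Only true recurrence remains, and if MACE are rare it barely matters.
- **That all adverse-event rates share the problem.** The Poisson rates in 9.10.1 are tabulated by single preferred term with no planned confidence interval, so there is no interval to be wrong.
- **That the SAP contradicts itself because 10.1 declares count data over-dispersed.** It only assumes an NB distribution. A specific section naming Poisson may depart from a general default.
- **That the code proves an unadjusted AESI model.** The code is a draft written around the relapse dataset, and 9.10.2.4.1 does not cite 10.1. Section 9.10.1 does cite it for its Poisson rates, so it is the natural place to look, but strictly the variance handling for AESIs is unspecified.
- **That the intervals are too narrow in every category.** With one record per episode and no heterogeneity, coverage is nominal. The infection category takes only serious or severe events, which may limit repeats.

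Two mitigating facts also stand. The relative risk and the hazard ratio beside the rate ratio are unaffected by recurrence or duplicate terms. And 9.1.1 treats tests beyond the primary and secondary endpoints as exploratory, so no alpha depends on these intervals. What remains is that the AESI rate-ratio interval is planned on recurrent, pooled events with no stated protection against clustering.

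**Conclusion.** The point holds for the AESI rate ratios and is conditional in size. Where events cluster within subjects, the nominal 95% interval from ordinary Poisson regression will be too narrow. Assuming variance inflation of 1.0 to 2.2, coverage runs from about 95% to about 81%. The more frequent categories, and those pooling overlapping terms, are the most exposed; very rare categories are hardly affected by recurrence. The range rests on assumed rates, dispersion and records per episode, and on reading the draft code in 10.1 as the intended model. Heavier assumptions would give lower coverage, but nothing in the SAP supports choosing them. The consequence is confined to descriptive safety intervals; no confirmatory conclusion changes. The correction is still worth making, because these intervals compare the arms on pre-defined risks and the change is small.

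**What to change.** In 9.10.2.4.1, specify for each AESI category a log-linear Poisson model on one count per subject, with log observation time as offset and a subject-level robust (sandwich) variance, for example through a REPEATED SUBJECT= statement in PROC GENMOD. Alternatively, use the NB model of 10.1, with the robust Poisson as the stated fallback on non-convergence. Keep the ordinary Poisson interval for categories with very few events, where a sandwich variance is unreliable and clustering by recurrence is negligible, and state the event count below which this applies. Because records are summed to one count per subject, the robust variance also covers several terms recorded for one episode. No change is needed for MACE or for the preferred-term rates in 9.10.1.

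The cost is about one line of code per model and somewhat wider safety intervals. No additional data are needed.

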5.5 Safety variables

5.5.1 Definition of treatment-emergency, baseline and change-from-baseline, last on treatment, follow-up assessments for safety variables

For all safety data analyses described in this SAP, baseline is considered to be the last valid assessment prior to first study drug intake.

For each individual safety variable, baseline is defined to be the last valid measurement available before the date and time of first dose intake of study treatment, unless otherwise specified. On days where study drug is initiated or re-initiated, the pre-dose assessment for that day is defined as the last non-missing assessment prior to the study drug intake on that day. The pre-dose assessment on Day 1 (if available) is identical to baseline; however, missing pre-dose data on Day 1 is not imputed with baseline. In case of (partially) missing assessment dates/times, or for assessments reported on Day 1 (or day of re-initiation) with recorded assessment time contradicting the time point label (e.g., pre-dose, 2 hours post-dose), the nominal visit and time point labels will be used to determine whether an assessment is considered for baseline (for example a blood pressure measurement with an assessment date on Day 1 but with a missing assessment time or an assessment time prior to the reported time of first study drug intake, will not be considered for baseline if reported under the time-point “2 hours post-dose” in the eCRF, however it will be considered if reported as “Pre-dose” in the eCRF).

Absolute changes from baseline are defined as post-baseline value minus baseline value, i.e., a positive sign indicates an increase compared to baseline.

A percentage change from baseline is defined as the absolute change from baseline divided by the baseline value (if the baseline value is > 0) and then multiplied by 100.

Absolute and percent change from baseline is calculated and stored for all continuous safety data.

In addition, the following assessments are flagged or derived per parameter:

- Last on-treatment assessment: Last assessment prior to or on EOT date +1 day)
- Day-15 follow-up, between EOT + 8 days and EOT + 22 days [see Section 11.4]
- Day-30 follow-up, between EOT + 23 days and EOT + 37 days [see Section 11.4]
- Last follow-up assessment: Last assessment between EOT + 8 and EOT + 37 days

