5.5.7 Adverse events leading to hospitalization

AEs leading to hospitalization are those where the eCRF question ‘Did the Adverse Event require subject hospitalization?’ is recorded as ‘Yes’ on the Adverse Event eCRF.

5.5.8 Adverse events on Day 1 and Day 1 of re-initiation of study treatment

Treatment-emergent AEs on Day 1 of study treatment are those AEs that start on or after study treatment start (on Day 1), by time and date, and before the following calendar date.

Treatment-emergent AEs on Day 1 of re-initiation of study treatment are those AEs that start on the date of a study treatment re-initiation.

Note: AEs in the first dose database with a different onset date than the first study drug intake or Day 1 of re-initiation of study treatment are not considered as ‘Day 1’ / ‘Day 1 of re-initiation of study treatment’ events.

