5.5.11.1 Quantitative ECG variables

Central reader ECG data contains the following quantitative measurements and derived variables: Heart rate (HR) (bpm), PR interval (ms), QRS duration (ms), RR interval (ms), QT interval (ms), QT_cB (ms) and QT_cF (ms). Heart rate is labeled “Mean heart rate” in the data transferred, however for consistency with earlier studies and to avoid misinterpretation as value coming from Holter monitoring, the label used in the CSR is “Heart rate”. Baseline is flagged and absolute and percent changes from baseline are calculated for each post-baseline value as described in Section 5.5.1. In the same manner, pre-dose values are flagged and absolute and percent changes from pre-dose are calculated for the hourly post-dose assessments after first dose on Day 1 or at re-initiation.

For by-visit and by-hour tables presenting summary statistics of quantitative ECG results, the latest (by date-time) transmitted measurement per nominal subject-visit/timepoint is used in case of multiple data available for a visit or visit/timepoint.

All assessments meeting the following conditions are flagged in the ADaM dataset:

- Heart rate \leq 50 bpm
- Heart rate \leq 45 bpm
- Heart rate \leq 40 bpm
- PR interval $>$ 200 ms and increase of $>$ 20 ms compared to baseline assessment
- QT_cF/QT_cB prolongations of $>$ 500 ms
- QT_cF/QT_cB prolongations of $>$ 480 ms
- QT_cF/QT_cB prolongations of $>$ 450 ms
- QT_cF/QT_cB increase from baseline $>$ 30 ms

- QTcF/QTcB increase from baseline > 60 ms
- QTcF/QTcB prolongations of > 500 ms and increase from baseline > 30 ms
- QTcF/QTcB prolongations of > 500 ms and increase from baseline > 60 ms
- QTcF/QTcB prolongations of > 450 ms and increase from baseline > 30 ms
- QTcF/QTcB prolongations of > 450 ms and increase from baseline > 60 ms

In addition, similar notable abnormality flags are derived in relation to the pre-dose measurements for the post-dose assessments on Day 1 and start of study drug re-initiation, and for the 3-hours post-dose measurement at Week 12 visit:

- PR interval > 200 ms and increase of > 20 ms compared to pre-dose assessment
- QTcF/QTcB increase from pre-dose assessment of > 30 ms
- QTcF/QTcB increase from pre-dose assessment of > 60 ms

For presentation of these outliers in by-visit and by-hour tables, the most extreme (i.e., lowest heart rate and highest interval) is considered in case of multiple data available at a visit or visit/timepoint.

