5.5.11.2 Qualitative ECG variables

Morphological ECG findings are reported by the central reader, and mapped to CDISC standard (codelist C71150, with high level categories from codelist C71152) in the SDTM.

For analyses in tables the following categories are anticipated:

- Atrioventricular Conduction
- Axis and Voltage
- Chamber Hypertrophy or Enlargement
- Conduction
- Ectopy
- Intraventricular-Intraatrial Conduction
- Rhythm Not Otherwise Specified
- ST Segment, T wave, and U wave
- Sinus Node Rhythms and Arrhythmias
- Supraventricular Arrhythmias
- Supraventricular Tachyarrhythmias
- Ventricular Arrhythmias

Findings related to interpretation or technical issues are only included in listings.

Morphological ECG findings are flagged as “New” if not present at any pre-treatment assessment (i.e. at any ECG assessed prior to the study treatment start) or “Pre-existing” if present at any pre-treatment assessment. In case of missing or non-evaluable pre-

treatment ECG assessment, it is conservatively assumed that any treatment-emergent morphological ECG finding is “New”.

For presentation of these findings in by-visit and by-hour tables, all reported abnormalities are considered in case of multiple assessments available at a visit or visit/timepoint.

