- Number and percentage of subjects with any treatment-emergent PR, QTcF prolongations and HR outliers together with 95% CIs for proportions (Clopper-Pearson exact method) are presented overall and by visit. Percentages are based on the number of subjects with at least one treatment emergent result available for the corresponding parameter. Abnormalities are presented cumulatively, i.e., a subject with a treatment emergent QTcF result > 500 ms is also summarized in the category QTcF > 450 ms;

- Number and percentage of subjects with any post-dose PR, QTcF prolongations and HR outliers on Day 1 or Day 1 of Re-initiation together with 95% CIs for proportions (Clopper-Pearson exact method) are presented overall post-dose hours and by individual time point. Percentages are based on the number of subjects with at least one post-dose result available for the corresponding parameter and time point. Abnormalities are presented cumulatively;
- Number and percentage of subjects with any 3-hr post-dose PR, QTcF prolongations and HR outliers on Day 1, Week 12 Visit, and Day 1 of any re-initiation together with 95% CIs for proportions (Clopper-Pearson exact method). For this analysis the ECG results reported as 3-hours post-dose are considered, irrespective of actual time the ECG was performed. Percentages are based on the number of subjects with a result available for the corresponding parameter at 3-hours post-dose. Abnormalities are presented cumulatively;
- Number and percentage of subjects with prior morphological ECG findings, and new/pre-existing treatment-emergent morphological ECG findings (at any time during the respective periods, i.e., prior or treatment-emergent), by abnormality and group term following CDISC terminology are presented. New (as compared to any assessment prior to study drug start) findings are also presented by visit;
- Number and percentage of subjects with prior and new/pre-existing morphological ECG findings on Day 1 or on Day 1 of any re-initiation, by abnormality and group term following CDISC terminology are presented. New (as compared to any assessment prior to study drug start) post-dose hourly ECG findings are also presented and by individual time point;
- Number and percentage of subjects with prior and new/pre-existing treatment-emergent morphological ECG findings at Visit 4 (Week 2), by abnormality and group term following CDISC terminology.

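### In the re-initiation tables, new ECG morphology is judged only against ECGs before first study drug and adverse events only by calendar date, so some pre-dose findings and events are counted as post-dose

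*SAP*

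**What the plan says.** **ECG morphology.** SAP Section 5.5.11.2 flags a morphological finding as new "if not present at any pre-treatment assessment (i.e. at any ECG assessed prior to the study treatment start"; otherwise it is pre-existing. Section 5.3.1 fixes study treatment start as the earliest documented study drug date, so the term cannot mean a later re-initiation dose. Section 9.10.3 carries this reference to re-initiation. It plans "Number and percentage of subjects with prior and new/pre-existing morphological ECG findings on Day 1 or on Day 1 of any re-initiation", and the same bullet continues: "New (as compared to any assessment prior to study drug start) post-dose hourly ECG findings are also presented and by individual time point".

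**Quantitative ECG and blood pressure.** Section 5.5.1 gives initiation and re-initiation days their own reference: "the pre-dose assessment for that day is defined as the last non-missing assessment prior to the study drug intake on that day". Section 5.5.11.1 uses it for ECG intervals and heart rate, where "changes from pre-dose are calculated for the hourly post-dose assessments after first dose on Day 1 or at re-initiation". It also derives PR and QTc flags relative to pre-dose at re-initiation. Section 5.5.10.1 treats blood pressure in the same way.

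**Adverse events.** Section 5.5.8 defines events on the original Day 1 as "those AEs that start on or after study treatment start (on Day 1), by time and date, and before the following calendar date". For restarts it says only: "Treatment-emergent AEs on Day 1 of re-initiation of study treatment are those AEs that start on the date of a study treatment re-initiation". No clock time is required.

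**The concern.** The re-initiation displays are where a reader will look for what happened after the restart dose. Section 2.1.1 gives reduction of the ponesimod first-dose effect as the reason for up-titrating at the start and again after an interruption of more than 3 days.

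On the original Day 1, ECGs before study treatment start include that day's pre-dose ECG, so the reference for morphology suits the purpose. At re-initiation the same reference skips everything that happened between first dose and restart. Persisting on-treatment findings then sit in the same rows as findings that appeared after the restart dose, and the summary table cannot separate them.

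The adverse event rule has a smaller version of the same problem. An event with a recorded onset before the restart dose on that date counts as a re-initiation event, although the matching rule on Day 1 would exclude it. The definition applies to the re-initiation tables for adverse events (Section 9.10.1), serious adverse events (9.10.2.2) and events leading to discontinuation (9.10.2.3).

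**Working it through.** There is no figure in the SAP to reproduce, so the check applies the written rules to defined cases.

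**ECG morphology.** The columns give the state of one finding at four points and then its post-dose class at re-initiation under two rules: the SAP rule (Sections 5.5.11.2 and 9.10.3) and a rule using that day's pre-dose ECG (the reference in Section 5.5.1).

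| Case | Before first dose | On treatment, earlier | Re-initiation, pre-dose | Re-initiation, post-dose | SAP rule | Pre-dose rule |
|---|---|---|---|---|---|---|
| A. Acquired on treatment, persisting | absent | present | present | present | new | not new |
| B. First seen after restart dose | absent | absent | absent | present | new | new |
| C. Seen on Day 1, resolved, recurs | absent | present | absent | present | new | new |
| D. Seen before treatment, absent at restart, recurs | present | any | absent | present | pre-existing | new |

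Case A is the misclassification: the finding precedes the restart dose but is tabulated as new after it. Cases A and B cannot be told apart in the planned table. Case D shows that the two rules can also differ in the other direction, so each answers a separate question.

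**Adverse events.** Take an illustrative onset at 07:00 and a dose at 09:00 on the same date.

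- If the dose is the first dose, Section 5.5.8 requires onset at or after treatment start by date and time. 07:00 is before 09:00, so the event is not counted.
- If the dose is a re-initiation dose, Section 5.5.8 requires only the same date. The event is counted.

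**Does another rule correct this?** The treatment-emergent time condition in Section 5.5.1 refers only to the first study treatment start. An event before a later restart dose passes it.

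**Is a time-based rule workable?** Section 12.3 sets a missing onset time to the re-initiation dosing time when the onset date is a documented re-initiation date. Untimed events would therefore still be counted.

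**The case against.** The strongest reply is that the reference is disclosed and deliberate. Section 9.10.3 states the comparator where it describes the output and uses it consistently across Day 1, re-initiation and scheduled visits. Comparison with the never-exposed state is a recognisable safety convention, and over-counting is the conservative direction. The effect of the restart dose on heart rate, PR, QTc and blood pressure is already measured against that day's pre-dose value. All ECG data and morphological findings are listed, so individual cases can be traced. Dosing is in the morning (Section 2.1.1), so the adverse event rule can misplace only onsets between midnight and the dose on one date.

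Much of this stands, and it limits the point. The existing classification is worth keeping, the quantitative analyses are sound, and the adverse event part is probably small. It does not remove the inconsistency. The same SAP uses the pre-dose reference for every other measure at re-initiation, and listings do not repair a summary table.

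Three stronger readings are not supported:

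- A reader might infer that the SAP attributes these findings to the restart dose. It makes no causal statement and only tabulates them.
- A reader might conclude that comparison with Day 1 is invalid. The SAP plans no formal comparison, and subjects who re-initiate are a subset formed after randomization, so any such comparison is informal in any case.
- A reader might want a finding called new at re-initiation only if it is absent on every earlier ECG. That would class case C as not new and hide a first-dose finding that resolved and recurred.

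**Conclusion.** The point holds as an inconsistency in descriptive safety tables that is worth correcting. In the Day 1 of re-initiation displays, morphological findings already present on that day's pre-dose ECG can be tabulated as new post-dose findings, and adverse events with onset earlier on the same date are counted. The morphology part carries most of the weight.

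The size cannot be determined. The SAP gives neither the number of re-initiations nor the frequency of findings acquired on treatment, and any percentage would be a guess. Any inflation would be larger in an arm with more persisting on-treatment findings, but the document does not show whether the arms differ in this.

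The conclusion rests on reading study treatment start as the first dose, as Section 5.3.1 defines it, and on Section 5.5.8 meaning what it says in omitting a time condition. The consequence is that the Day 1 and re-initiation displays are not like for like. Quantitative ECG changes, the PR and QTc flags against pre-dose, and all efficacy analyses are unaffected.

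**What to change.** 1. In Section 5.5.11.2, add a flag for each re-initiation day that classes a post-dose morphological finding as new if it is absent on that day's pre-dose ECG, using the pre-dose definition in Section 5.5.1. State how a missing pre-dose ECG is handled; the conservative convention already in Section 5.5.11.2 would serve.
2. In Section 9.10.3, tabulate this flag for Day 1 of re-initiation beside the existing classification against pre-treatment ECGs. Keep the existing classification unchanged for Day 1 and scheduled visits.
3. In Section 5.5.8, count an adverse event on Day 1 of re-initiation only if its onset date and time are at or after the re-initiation dose, with missing times set to the dosing time as Section 12.3 already provides. State whether the same rule governs the first day in the Section 9.10.2.4.1 display of heart rate and rhythm events by day after re-initiation.

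The cost is SAP wording, one extra flag in each of the ECG and adverse event datasets, and one added set of columns or rows. No new data are needed, because the pre-dose and timing concepts are already defined.
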